1.2 Secondary Aims

1.2.1 To assess the feasibility and toxicity profile of CDX-011 in patients with recurrent osteosarcoma.

1.2.2 To describe the pharmacokinetics of CDX-011 in adolescents and young adults with recurrent osteosarcoma enrolled at COG sites and COG Phase 1 Consortium sites only.

1.2.3 To determine if there is a relationship between tumor GPNMB expression by IHC and response to CDX-011 therapy.

1.2.4 To estimate, in the cohort of patients previously treated with eribulin, the proportion who will experience disease progression during the first 4 months of CDX-011 therapy and the proportion of patients who experience a RECIST-defined complete or partial response.

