2.0 BACKGROUND

2.1 Introduction/Rationale for Development

The outcome of patients with newly diagnosed, localized osteosarcoma improved following the addition of multi-agent chemotherapy to complete surgical resection.^{1,2} Current results in contemporary cooperative group studies reveal 3-year event-free survival (EFS) ranging between 50-75%.³⁻⁶ Cisplatin^{7,8} and doxorubicin^{9,10} are the most active agents, and standard chemotherapy includes the use of these two agents alone^{5,11} or in combination with high-dose methotrexate^{6,12} and/or ifosfamide.^{4,12-14} The prognosis is poor for the 30-40% of patients who develop recurrent disease,¹⁵ as well as for those with clinically detectable metastases at the time of initial diagnosis^{6,13,16} with 2-year survival rates of 20-30%.^{4,6,13,16-21}

The aggregate EFS for patients with recurrent osteosarcoma enrolled on seven closed Phase 2 studies from the COG or its predecessor groups is poor, with an overall 12% EFS at 4 months [95% CI: 6.0%-19%].

Due to the lack of progress seen in treatment of osteosarcoma over the past 25 years and overall poor prognosis for children, adolescents and young adults with recurrent or refractory osteosarcoma, novel treatment strategies are needed.

CDX-011 is an antibody drug conjugate (ADC) directed against Glycoprotein non-metastatic B. The preclinical data that establishes the rationale for proceeding with a Phase 2 evaluation in patients with relapsed or refractory osteosarcoma is described below.

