9.0 STATISTICAL CONSIDERATIONS

9.1 Sample Size and Study Duration

A review of enrollment on COG single-agent Phase 2 studies demonstrates that approximately 1.8 patients per month will potentially be eligible for AOST1521. A maximum of 29 outcome evaluable patients will be required for the evaluation of CDX-011 amongst patients without prior treatment with eribulin. Eribulin has not been used as a component of therapy for newly diagnosed patients in pediatric protocols and there has been only one COG study of that agent for patients with recurrent disease. As such, we expected no more than 15% of patients who are eligible for this study to have received eribulin as part of therapy prior to potential enrollment on this study. Providing for possible ineligible and inevaluable patients, the maximum enrollment will be 38 patients.

With these entry rates, the probability we will accrue at least 38 patients in 24 months is 80% and the corresponding probability for 30 months is in excess of 99%. The study will likely require 2 to 2.5 years to enroll sufficient patients. A maximum of 38 patients is anticipated.

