9.2 Study Design

Feasibility Cohort: The first six (6) younger patients (< 18 years of age) who are evaluable for toxicity will be considered as the feasibility cohort. All such patients will be assigned to receive 1.9 mg/kg/dose. Enrollment to this cohort will not be segregated by prior treatment with eribulin. Study accrual will be suspended after the sixth patient is enrolled; enrollment of patients 18 years of age or older will continue regardless of the result in the feasibility cohort. If dose limiting toxicity (DLT) during the first cycle of therapy occurs in one or fewer evaluable patients then the trial accrual will proceed as outlined below. Patients who are enrolled in the toxicity cohort who receive the “feasible” dose of CDX-011 will be considered in the outcome evaluation rules presented below for the relevant patient stratum as it relates to prior eribulin exposure.

Patients will be enrolled in two stages. In the first stage, 19 disease control and RECIST response evaluable patients will be enrolled. Each patient will be evaluated for both outcome measures: (1) disease control success; and (2) RECIST response (CR or PR v. not CR or PR). The decision rule for the two stage study design is summarized as:

Stage	Number of Patients Enrolled in Stage	Cumulative Response Results	Decision
I	19	4 or fewer disease control successes	Terminate the trial with the conclusion that Glembatumumab

		and 1 or fewer RECIST responders	Vedotin is not associated with sufficient activity for further single agent investigation
		5 or more disease control success or 2 or more RECIST responders	Continue to stage II
II	10	8 or fewer disease control successes and 4 or fewer RECIST responders	Terminate the trial with the conclusion that Glembatumumab Vedotin is not associated with sufficient activity for further single agent investigation
		9 or more disease control successes or 5 or more RECIST responders	Terminate the trial with the conclusion that Glembatumumab Vedotin is associated with sufficient activity for further single agent investigation

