Design Characteristics: Each patient enrolled will be evaluated for: (1) complete or partial response as defined by the RECIST criteria where the first evaluation of CR or PR is made at or before the end of the sixth cycle of study therapy (denoted as R below); or (2) stable disease after four months of therapy or at the end of the sixth cycle, whichever occurs first (denoted as S below). We will not be interested in promoting the agent for further investigation if the probability of response in any particular individual is less than or equal to 0.05 ($P(R) \leq 0.05$) and the probability of remaining analytic event free in any particular individual is less than or equal to 0.20 ($P(S) \leq 0.20$). We will be interested in promoting the agent for further investigation if the probability of response in any particular individual is at least 0.22 ($P(R) \geq 0.22$) **or** the probability of remaining analytic event free in any particular individual is at least 0.42 ($P(S) \geq 0.42$).

For the calculations below, it is assumed $\Pr(S|R) = 0.90$.

The statistical characteristics of this design are:

Probability of four month disease control	Probability of RECIST response	Probability of Stopping After Stage 1 (and concluding the drug is ineffective)	Probability of Concluding the Drug is Ineffective at the Conclusion of the Trial	Probability of Concluding the Drug is Effective at the Conclusion of the Trial
0.20	0.05	0.56	0.89	0.11
0.42	0.22	0.014	0.05	0.95
0.42	0.05	0.044	0.096	0.904
0.20	0.22	0.056	0.21	0.79

Prior Treatment with Eribulin: As noted in [Section 9.1](#), we expect no more than 15% of patients will have been treated with eribulin prior to enrollment on AOST1521. Patients will be evaluated for S and R as described above. Enrollment to this stratum will be terminated when we can determine there are sufficient patients to fully evaluate the efficacy of CDX-011 in the stratum of patients without prior eribulin therapy. If 19 patients with prior eribulin therapy are enrolled, the staged design described above for patients without prior eribulin therapy will be applied to this stratum.

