Patients who are not evaluable for both disease control and response evaluation may be replaced for the purposes of the statistical rule.

9.5 **Evaluability for Toxicity**

Tolerability of CDX-011 - An eligible patient will be considered for toxicity monitoring if one of the following occurs: (1) complete one cycle of CDX-011 prior to receiving non-protocol anticancer therapy; (2) die on protocol therapy for a reason considered possibly, probably or likely related to CDX-011; or (3) are removed from protocol therapy because of an adverse experience possibly, probably or likely related to CDX-011. A toxicity-evaluable patient will be considered in the analysis during the interval from study enrollment until the termination of protocol therapy. A toxicity-evaluable patient will be considered to have experienced an excessive toxicity event if: (1) the patient dies on protocol therapy for a reason considered possibly, probably or likely related to; or (2) experiences a dose-limiting toxicity (DLT). DLTs will be as defined in [Section 5.1.1](#) of the protocol:

The analytic unit for monitoring for excessive toxicity will be the patient-cycle: Each cycle where the patient receives CDX-011 and does not receive non-protocol anticancer therapy will be considered in the analysis. If there is overwhelming evidence that the dose selected for this trial has a per-cycle-DLT probability of more than 30%, we will identify the regimen to the COG DSMC, Bone Tumor Committee leadership and CTEP as associated with a toxicity profile that may require modification of the regimen. We will use a Bayesian rule to monitor for excessive toxicity. We will assume a beta prior to distribution with $\alpha=0.6$ and $\beta=1.4$. If this posterior probability of the chance of DLT is at least 30% exceeds 80%, we will identify the regimen to the COG DSMC, Bone Tumor leadership and CTEP as associated with a toxicity profile that may require modification of the regimen.

9.6 **Estimation of Disease Control and RECIST Response Rates**

$P(R)$ and $P(S)$ for each cohort defined by prior eribulin exposure will be estimated using the maximum likelihood estimates, *viz.*,

$$P(R) \hat{=} \hat{p}_R = \frac{\text{Number of Patients Considered as PR or CR}}{\text{Number of Evaluable Patients in Cohort}};$$

$$P(S) \hat{=} \hat{p}_S = \frac{\text{Number of Patients With Disease Control at 4 Months}}{\text{Number of Evaluable Patients in Cohort}}$$

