Confidence intervals will be constructed using the approximate normal distribution of each of the estimates and their asymptotic variances:

$$V(\hat{p}_R) \hat{=} \frac{\hat{p}_R(1-\hat{p}_R)}{\text{Number of Evaluable Patients in Cohort}};$$

$$V(\hat{p}_S) \hat{=} \frac{\hat{p}_S(1-\hat{p}_S)}{\text{Number of Evaluable Patients in Cohort}}$$

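### The normal-approximation intervals in Section 9.6 fail for response rates near 5%: coverage is 65–76% at an assumed 95% level, and every stage 1 stop gives a zero-width interval or a negative lower limit

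*Combined protocol and SAP*

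**What the plan says.** Section 9.6 takes the rates P(R) (RECIST response) and P(S) (disease control) as raw proportions, "for each cohort defined by prior eribulin exposure will be estimated using the maximum likelihood estimates". It then states: "Confidence intervals will be constructed using the approximate normal distribution of each of the estimates and their asymptotic variances". The variance printed for each is p̂(1 − p̂) divided by the number of evaluable patients in the cohort, so the method is the Wald interval. The section gives no confidence level, no rule for a count of zero, no truncation at zero, no exact or score alternative, and no adjustment for the two-stage design.

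The counts to which this formula will be applied follow from the rest of Section 9:

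- Section 9.1: "A maximum of 29 outcome evaluable patients will be required" in the group without prior eribulin.
- Section 9.2, decision table: 19 patients in stage 1 and 10 more in stage II. The trial stops after stage 1 only with 4 or fewer disease control successes "and 1 or fewer RECIST responders".
- Section 9.2, Design Characteristics: the agent is of no interest "if the probability of response in any particular individual is less than or equal to 0.05" and P(S) is 0.20 or lower. It is of interest if P(R) reaches 0.22 or P(S) reaches 0.42.

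Aim 1.2.4 applies the same estimates to the prior-eribulin group: "To estimate, in the cohort of patients previously treated with eribulin, the proportion who will experience disease progression", together with the proportion who respond. Section 9.1 expects that group to be at most 15% of eligible patients.

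**The concern.** A normal approximation to a binomial proportion needs a reasonable number of events. At a 5% response rate the expected number of responders is 19 × 0.05 = 0.95 at stage 1 and 29 × 0.05 = 1.45 at full size. At those counts the Wald interval collapses to a point when nobody responds, and its upper limit is too low when one to three patients do.

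These are the only intervals the plan specifies for the rates in Aims 1.1.1 and 1.2.4. When an agent looks inactive, the upper limit is what the reader needs, because it shows which response rates remain compatible with the data. A zero-width interval claims certainty that the trial does not have.

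**Working it through.** **Inputs.** From Section 9.2: stage sizes 19 and 10; stop if S ≤ 4 and R ≤ 1; final positive conclusion if S ≥ 9 or R ≥ 5 of 29; design values P(S) = 0.20 or 0.42 and P(R) = 0.05 or 0.22; Pr(S|R) = 0.90. From Section 9.6: p̂ ± z·√(p̂(1 − p̂)/n). The confidence level is assumed to be two-sided 95% (z = 1.96), the level Section 2.1 uses for its historical benchmark ("with an overall 12% EFS at 4 months [95% CI: 6.0%-19"%]).

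**Step 1: reproduce the plan's table.** Each patient falls into one of four cells: responder with disease control, 0.9·P(R); responder without, 0.1·P(R); disease control without response, P(S) − 0.9·P(R); neither, the remainder. At (0.20, 0.05) these are 0.045, 0.005, 0.155 and 0.795. Exact enumeration through 19 and then 10 more patients gives:

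| P(S), P(R) | Stop after stage 1: plan / computed | Conclude effective: plan / computed |
|---|---|---|
| 0.20, 0.05 | 0.56 / 0.564 | 0.11 / 0.108 |
| 0.42, 0.22 | 0.014 / 0.0135 | 0.95 / 0.949 |
| 0.42, 0.05 | 0.044 / 0.0448 | 0.904 / 0.904 |
| 0.20, 0.22 | 0.056 / 0.0566 | 0.79 / 0.789 |

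**Step 2: intervals at the likely counts.** For 1/19, p̂ = 0.0526, the standard error is √(0.0526 × 0.9474/19) = 0.0512, and the interval is 0.0526 ± 1.96 × 0.0512.

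| Responders | Wald 95% | Exact (Clopper-Pearson) 95% |
|---|---|---|
| 0/19 | 0 to 0 | 0 to 17.6% |
| 1/19 | -4.8% to 15.3% | 0.1% to 26.0% |
| 0/29 | 0 to 0 | 0 to 11.9% |
| 1/29 | -3.2% to 10.1% | 0.1% to 17.8% |
| 2/29 | -2.3% to 16.1% | 0.8% to 22.8% |
| 3/29 | -0.7% to 21.4% | 2.2% to 27.4% |

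The first two rows are the only response counts possible at a stage 1 stop. The lower limit at 1/19 is negative at any level above about 70%, since p̂/SE = 1.03. At 1/19, 2/29 and 3/29 the Wald interval excludes the plan's 22% rate of interest and the exact interval does not.

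**Step 3: how often this happens at (0.20, 0.05).**

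- Stop with 0 responders: 0.95^19 × Pr(Bin(19, 0.155/0.95) ≤ 4) = 0.3774 × 0.8132 = 0.307.
- Stop with 1 responder: 0.257. The two sum to the stop probability, 0.564. Given a stop, the chance of a zero-width interval is 0.307/0.564 = 54%.
- Continue and finish with 0 of 29: 0.042. The zero-width total is 0.307 + 0.042 = 34.9%.
- Negative lower limit: 0.257 at stage 1 plus 0.342 with 1 to 3 of 29 = 59.9%.

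**Step 4: coverage.** Add the probability of every outcome whose interval contains the true rate, with n = 19 if stopped and n = 29 otherwise.

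| P(S), P(R) | Wald, response | Exact, response | Wald, disease control | Exact, disease control |
|---|---|---|---|---|
| 0.20, 0.05 | 64.8% | 98.7% | 89.7% | 96.6% |
| 0.42, 0.05 | 76.0% | 98.6% | 91.5% | 95.8% |
| 0.42, 0.22 | 88.9% | 97.7% | 93.3% | 96.0% |
| 0.20, 0.22 | 87.4% | 97.6% | 89.8% | 96.4% |

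**Step 5: sensitivity.** A zero count gives a zero-width interval at any confidence level, so coverage at (0.20, 0.05) cannot exceed 1 − 0.349 = 65.1%; at a 90% level it is 63.8%. Varying Pr(S|R) from 0.5 to 1.0 moves the two 5% figures only to 64.6–66.0% and 75.9–76.3%. With n fixed, Wald coverage at P(R) = 0.05 is 62.1% for 19 patients and 77.1% for 29, so the cause is the interval formula and not the stopping rule.

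**Step 6: prior-eribulin stratum.** Its size and response rate are not given. Assuming a 5% rate, the chance of a zero-width interval is 0.95^n: 86% at n = 3, 74% at n = 6 (about 15% of 38) and 38% at n = 19.

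**The case against.** The strongest reply is that no decision depends on these intervals. The go/no-go rule uses counts, no interval is compared with 5%, 22%, 20% or 42%, and an analyst could report an exact interval beside the planned one. That is true and limits the point to reporting. It does not make the planned interval usable, and the plan specifies no other for these rates.

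A second reply is that cutting a negative limit at zero is common and not forbidden. The plan does not state that convention. It would remove the impossible value but leave the zero-width interval and the short upper limit, which is still 15.3% against 26.0% at 1/19.

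Third, poor coverage and the zero-width interval are largely one defect: at (0.20, 0.05), 34.9 of the 35.2 points of non-coverage come from zero counts. This is correct, and they should not be counted as two failures. The negative lower limits cost almost no coverage there; their harm is the short upper limit.

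Fourth, the count at a stage 1 stop could exceed 19 if accrual runs on. Little changes, because one to three responders give a negative 95% lower limit whenever n is 14 or more.

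Finally, Clopper-Pearson is conservative, and a Wilson interval would also serve at P(R) = 0.05 (94.9% and 94.6% coverage). That concerns which remedy to choose and does not defend the present method. The eribulin-stratum figures are illustrative only.

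**Conclusion.** The concern holds. For response rates near 5%, the interval in Section 9.6 covers the truth 64.8–76.0% of the time at an assumed 95% level, and every stage 1 termination at 19 patients yields a zero-width interval or a negative lower limit. Coverage at a 22% response rate is 87–89%. The shortfall for disease control is mild, at 90–93%.

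The figures rest on the plan's own design values and Pr(S|R) = 0.90, with 19 patients at a stop and 29 otherwise. The 95% level is an assumption, but the failure does not depend on it. Type I error, power, sample size and the decision rule are unaffected. This should be fixed because it concerns the reported precision of a primary-aim rate.

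**What to change.** In Section 9.6, replace the normal-approximation sentence and delete both asymptotic variance formulas. Suggested text: *Two-sided 95% exact (Clopper-Pearson) confidence intervals will be reported for P(R) and P(S) in each cohort.* This also supplies the missing confidence level.

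No further adjustment for the two-stage design is needed to keep at least 95% coverage in the four design scenarios.

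The change needs one sentence and no added data. The cost is width: at 95% the exact interval is wider than Wald at every possible count for n = 19 and n = 29, for example 29.9 against 27.5 percentage points at 5/29 and 35.5 against 33.7 at 9/29.

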9.7 Statistical Considerations for Secondary Aim 1.2.3

9.7.1 *To determine the relationship of GPNMB expression by IHC to response in tumor specimens from patients:* Submission of archival tissue will be required for this study. The primary cohort to address this aim will be the patients who were not previously treated with eribulin. The GPNMB expression IHC result will be coded as an integer between 0 and 3 with 0 being no GPNMB expression and 3 indicating strong GPNMB expression. The outcome measure will be DC success (Yes v. No). Logistic regression using the categorical IHC result will be fitted to the data. The fitted coefficients from the logistic regression, and the p-value for the test of the hypothesis of no relationship between IHC result and probability of DC success will be used to characterize this secondary analysis. Trend will also be assessed using the actual IHC numerical value.

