2.2 Preclinical Studies

The activity of CDX-011 in pediatric tumors was recently investigated through the Pediatric Preclinical Testing Program. GPNMB gene expression was evaluated in a variety of solid tumor and leukemia xenograft models. Given the consistent expression of GPNMB in the osteosarcoma xenografts, the *in vivo* anti-tumor activity was investigated in 6 female CB-17SC mice bearing osteosarcoma. The mice received 2.5 mg/kg of CDX-011 IV weekly for 3 doses, followed by 3 weeks of observation. Complete tumor responses were seen in 3/6 osteosarcoma xenografts. Of the 3 responding xenografts, 2 had the highest levels of GPNMB expression. The lowest GPNMB-expressing osteosarcoma xenograft had minimal response to CDX-011 treatment (Figure 1).^{[23,45](#)} GPNMB protein expression through immunohistochemistry and by enzyme-linked immunosorbent assay (ELISA) has

also been assessed in human osteosarcoma cell lines. Sixty-seven human osteosarcoma samples were tested and 92.5% of osteosarcoma samples expressed GPNMB. CDX-011 induced cytotoxic effects in 74% of osteosarcoma cell lines and GPNMB protein levels correlated with CDX-011 *in vitro* cytotoxicity.⁴⁶

[figure not shown]

Figure 1. CDX-011 *in vivo* objective response activity for osteosarcoma models. Kaplan-Meier curves for EFS (left), median relative tumor volume graphs (center), and individual tumor volume graphs (right) are shown for selected lines. Treated (black lines), statistical significance (P values) of the difference between treated and control groups are included.

2.3

In this trial a tumor sample to test for GPNMB expression by immunohistochemistry (IHC), similar to the previous breast cancer and melanoma clinical trials, will be required. This will allow us to determine if higher levels of GPNMB expression by IHC correlates with tumor response to CDX-011 in osteosarcoma patients.

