9.4 Evaluability for Disease Control and Response

Which Patients will be Considered Evaluable for RECIST Response:

Any eligible patient who receives at least one dose of CDX-011 will be considered evaluable for response with the following exception: if a patient receives non-protocol anti-cancer therapy during the response evaluation period after the patient is considered as having a partial or complete response but prior to confirmation of this status by tumor imaging and before progressive disease is noted, the individual will be considered inevaluable for the response endpoint. Further, patients who stop CDX-011 after the 1st evaluation because of toxicities or death will be considered evaluable for the response evaluation and will be counted as non-responders for the response endpoint.

Which Patients Will Be Considered Evaluable for Disease Control Success:

Any eligible patient who receives at least one dose of CDX-011 will be considered evaluable for response with the following exception: if a patient receives non-protocol anti-cancer therapy during the first four months of therapy or first six cycles of therapy, whichever occurs first, is considered as having a partial or complete response but prior to confirmation of this status by tumor imaging and before progressive disease is noted, the individual will be considered inevaluable for the disease control success endpoint.

Which Patients Will be Considered a Disease Control Success:

Any patient who is evaluated free of all detectable disease (complete response) or is considered as having a partial response or is considered as having stable disease ('at least stable disease') after four months of therapy or at the end of the sixth cycle, whichever occurs first.

Which Patients Will be Considered Not a Disease Control Success:

Any evaluable patient who does not meet the criteria for disease control success (complete response, partial response or stable disease) will be considered to not have experienced disease control success.

In particular, any patient who dies because of treatment-related toxicity during the first six cycles of therapy and within the first four months since starting treatment will be

considered not to have experienced disease control success. Also, any patient who is eligible, receives one dose of CDX-011 and is lost to follow-up at (for example) the end of cycle 2 will be considered not a disease control success (complete response, partial response or stable disease).

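### Section 9.7.1 relates GPNMB expression only to disease control success, so no analysis of GPNMB against RECIST response is planned although Aim 1.2.3 refers to response

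*Combined protocol and SAP*

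**What the plan says.** Three places describe the biomarker question in terms of response.

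- Aim 1.2.3 is "To determine if there is a relationship between tumor GPNMB expression by IHC and response to CDX-011 therapy".
- Section 2.3 says that the mandatory tumor sample will show "if higher levels of GPNMB expression by IHC correlates with tumor response to CDX-011 in osteosarcoma patients".
- The heading sentence of section 9.7.1 likewise speaks of the relationship of expression to response.

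The method in 9.7.1 names a single outcome: "The outcome measure will be DC success (Yes v. No". The logistic regression on the IHC category is fitted to it, and no other outcome is named for the trend assessment on the 0 to 3 score. The primary cohort is the patients without prior eribulin, at most 29 evaluable (section 9.1).

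Elsewhere section 9 keeps two endpoints apart. Section 9.2 says "Each patient will be evaluated for both outcome measures: (1) disease control success; and (2) RECIST response (CR or PR v. not CR or PR". It denotes by R a "complete or partial response as defined by the RECIST criteria where the first evaluation of CR or PR is made at or before the end" (the cut-off being Cycle 6), and by S the disease control endpoint. Section 9.4 counts as a DC success a patient who has a complete or partial response or who "is considered as having stable disease ('at least stable disease') after four months of therapy or at the end of the sixth cycle" (the earlier of the two). Section 9.6 estimates P(R) and P(S) separately.

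**The concern.** The aim and its analysis name different things. A patient whose tumor did not shrink but did not progress by four months is a success in 9.7.1. A responder who has progressed by that assessment is a failure. If most DC successes are stable disease, a fitted IHC coefficient mainly describes who stayed stable. In a single-arm trial that may partly reflect growth rate rather than drug effect.

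What is at stake is the reading of the result. With only the planned analysis, a report could present a DC association as evidence that GPNMB expression predicts tumor response, or a null DC result as evidence that it does not. Neither statement would be supported.

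**Working it through.** **1. Confirm what S contains.** Section 9.2 gives P(S), P(R) and Pr(S|R) = 0.90. If S includes responders, each patient falls in one of these cells:

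- S and R: 0.9 × P(R)
- R, not S: 0.1 × P(R)
- S, not R (stable disease only): P(S) − 0.9 × P(R)
- neither: the remainder

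Apply the 19 + 10 rule exactly: stop if S ≤ 4 and R ≤ 1 at stage 1; declare activity if S ≥ 9 or R ≥ 5 at the end.

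| P(S) / P(R) | Stop at stage 1: plan | Recomputed | Effective: plan | Recomputed |
|---|---|---|---|---|
| 0.20 / 0.05 | 0.56 | 0.564 | 0.11 | 0.108 |
| 0.42 / 0.22 | 0.014 | 0.0135 | 0.95 | 0.949 |
| 0.42 / 0.05 | 0.044 | 0.045 | 0.904 | 0.904 |
| 0.20 / 0.22 | 0.056 | 0.057 | 0.79 | 0.789 |

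The plan's table reproduces to rounding, so these cells are the ones the plan used.

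**2. Share of DC successes that are stable disease only.** Formula: [P(S) − 0.9 × P(R)] / P(S). Expected counts are out of 29.

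| P(S) / P(R) | Calculation | Stable only | DC successes | Responders |
|---|---|---|---|---|
| 0.20 / 0.05 | (0.20 − 0.045) / 0.20 | 78% | 5.8 | 1.5 |
| 0.42 / 0.22 | (0.42 − 0.198) / 0.42 | 53% | 12.2 | 6.4 |
| 0.42 / 0.05 | (0.42 − 0.045) / 0.42 | 89% | 12.2 | 1.5 |
| 0.20 / 0.22 | (0.20 − 0.198) / 0.20 | 1% | 5.8 | 6.4 |

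The 53% depends on the overlap: it is 58% at Pr(S|R) = 0.80 and 48% at 1.00. Responders coded as DC failures number 0.1 × 1.5 = 0.15 to 0.1 × 6.4 = 0.64 patients, which is negligible.

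**3. Does using S lose or gain power?** The documents give neither an IHC distribution nor response rates by IHC level, so these are assumptions: IHC 0/1/2/3 shares of 7.5/25/35/32.5% and response rates of 0/6/20/42%. Overall R is 0.25 × 0.06 + 0.35 × 0.20 + 0.325 × 0.42 = 0.22. Overall S is held at 0.42, n = 29, with a one-sided 2.5% trend test, by simulation.

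- *Stable disease among non-responders unrelated to IHC.* Its rate is (0.42 − 0.9 × 0.2215) / (1 − 0.2215) = 0.28 at every level. Power is about 0.49 for R and 0.16 for S.
- *Stable disease among non-responders proportional to IHC score.* The rate per score point is 0.22065 / (0.25 × 0.94 × 1 + 0.35 × 0.80 × 2 + 0.325 × 0.58 × 3) = 0.22065 / 1.3605 = 0.16, so rates are 0, 0.16, 0.32 and 0.49. Power is about 0.49 for R and 0.67 for S.
- *Weaker gradient, 8% to 40%.* The two outcomes are about equal (0.47 against 0.44).

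The ranking turns on a quantity that the documents do not give.

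**4. Where R can be analysed at all.** At P(R) = 0.05 the chance of no responder is 0.95^29 = 23% with 29 patients, and 0.95^19 = 38% if the trial stops at 19. With IHC split in half (14 against 15), response 3 to 10 times higher in the high group and stable disease unrelated to IHC, Fisher exact power at P(R) = 0.05 is under 4% for either outcome.

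**The case against.** The best defence is that response is used loosely in this protocol. The disease-control paragraph of section 9.4 speaks of patients evaluable for response, and the decision table in 9.2 puts both endpoints under one response heading. Where only CR/PR is meant, some aims say so (1.1.1 and 1.2.4). On that view 9.7.1 simply fixes what 1.2.3 means, using one of the two primary endpoints. This has some force, but usage is not uniform: section 2.3 says tumor response, and 9.2 uses the bare word for R. The ambiguity still needs settling.

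A reader might infer three stronger things.

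- *That DC success dilutes a true GPNMB effect.* This holds only if stable disease is not itself linked to GPNMB. Step 3 shows the ranking reversing when it is.
- *That RECIST response should replace DC success.* At P(R) = 0.05 this would put about 1.5 events into a four-level logistic model, in place of 6 to 12 DC successes. The stable-only share is largest exactly where R is least analysable.
- *That the 12% historical 4-month EFS shows disease control without drug effect.* Section 2.1 takes that figure from patients on seven Phase 2 studies. It is not an untreated rate.

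Nor is the preclinical rationale purely about regression, since Figure 1 also reports EFS curves.

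**Conclusion.** The mismatch stands: the stated question is about response, the only planned outcome is DC success, and no analysis of GPNMB against CR/PR is planned in the text available. At the plan's own rates and Pr(S|R) = 0.90, DC successes are stable disease only in 78%, 53%, 89% and 1% of cases, so a DC association cannot by itself be reported as a relation to tumor response.

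The documents do not support saying that the planned analysis is underpowered relative to one on R. That depends on assumed IHC shares, assumed response rates and an unknown link between stable disease and GPNMB. DC success remains a legitimate outcome. This is a secondary aim, and the primary decision rule does not change.

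**What to change.** In section 9.7.1:

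- Keep DC success as an outcome, with its current analysis.
- Add RECIST response, R as defined in 9.2, as a second and separately labelled outcome. Tabulate it by IHC score and use an exact trend test rather than a four-level logistic model.
- State that a DC association will not be reported as a relation to response.
- Optionally, as exploratory, describe best percent change in the sum of target-lesion diameters by IHC score. It would need a definition, and it does not capture progression by new lesions or disease that section 10.2.1.3 classes as non-measurable.

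The cost is a wording change and one extra test on a secondary aim. RECIST status is already needed for the primary endpoint, so no new patient procedure is required. The limitation should be written down: with a response rate near 5%, about 1.5 responders are expected in 29 and the R analysis will be uninformative.
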